# 3. Study Design

# 3.1. Eligibility Criteria

# 3.1.1. Inclusion Criteria

Infants: Infants who are born at Prentice Women's Hospital between 30 0/7 and 36 6/7 weeks gestation, are ≤20 days old at the time of enrollment, and do not meet any of the study's exclusion criteria will be eligible for participation in this study. Additionally, infants will only be included in this study if both of their biological parents are eligible and agree to participate.

Parents: Parents who are  $\geq$ 18 years of age, English speaking, expect mother and father to raise the infant together in the same household regardless of their marital status, and do not meet any of the study's exclusion criteria will be eligible for participation in this study. Additionally, family units will only be included in this study if both biological parents of the infant are eligible and agree to participate.

Only English speaking parents will be included in this trial because the study questionnaires are only available in English.

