# 1. Background and Significance

Among 4 million infants born annually in the US, nearly 0.5 million are born prematurely (<37 weeks gestation) and cared for in Neonatal Intensive Care Units (NICUs). These preterm infants are extremely vulnerable in the perinatal period, with increased risks of physiologic instability, apnea, chronic intermittent hypoxemia, impaired temperature and metabolic regulation, and infection (1-7). Such prematurity-related complications are the leading cause of neonatal mortality and morbidity and result in longer average lengths of hospital stay and higher rates of re-hospitalization in preterm infants than in full term infants. Strategies to improve the physiologic stability and maturation of preterm infants during the critical perinatal period are vital to improve preterm infant outcomes, reduce life-long morbidity, and mitigate associated healthcare costs.

Skin-to-skin contact between a preterm infant and a parent, also known as kangaroo care (KC), is an important, inexpensive modality deployed in the NICU to support the infant's development and the formation of the parent-infant bond. During KC, a parent holds an infant against their bare chest, skin-to-skin. NICU implementation of KC typically involves the mother (8), in a practice familiarly termed Kangaroo Mother Care (KMC). Over 1,000 articles supporting the implementation and positive effects of KMC have been published, outlining the positive effects of KMC intervention on physiologic and psychosocial outcomes. KMC is invaluable in promoting strong mother-infant bonds, reducing morbidity and mortality, improving infant physiologic stability, and benefiting overall development trajectories. Additionally, KMC has also been shown to greatly benefit mothers, with improved initiation and duration of breastfeeding, reduced anxiety, and improved sense of confidence in parenting (10).

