# 2.2. Outcome Measures

## 2.2.1. Primary Outcome

Primary outcome measures include heart rate (HR) and oxygen saturation (SpO2) as indicators of cardiorespiratory stability in infants before, during, and after KC and HR and HR variability (HRV) as indicators of physiologic stress in NICU parents during and after periods of KC. All of these outcomes will be measured using wearable, wireless biosensors.

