### 3.1.2. Exclusion Criteria

Infants: Infants who are intubated or sedated, are receiving vasopressors or analgesics, have any congenital anomalies or skin abnormalities deemed likely to impact KC by clinical team, have received or are planned to receive surgical intervention that will impact the utilization of KC, wearable sensors, and/or oral swabs, or are experiencing other symptoms or receiving other intervention that will impact the utilization of KC, wearable sensors, and/or oral swabs will be excluded from this study.

Parents: Parents who are showing any signs of illness or taking corticosteroids or testosterone supplementation will be excluded from this study. Non-English speaking parents will also be excluded from this study because the questionnaires associated with this study are only available in English.

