#### Kangaroo Care (KC) Intervention:

After enrollment, families will be scheduled to participate in two sessions of KC. The goal will be to schedule the KC sessions over two sequential days and at approximately the same time of day (i.e. morning, afternoon, or evening). However, if this is not possible given the parents' schedules, the sessions will be scheduled for the days and time of day that participating parents are able to visit their infant in the NICU. Each session will include two hours of continuous KC, with one day focused on Kangaroo Mother Care (KMC) and the other on Kangaroo Father Care (KFC), in a randomized order. These sessions will include continuous skin-to-skin holding of the infant by the parent, per standard of care protocol.

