#### Saliva Sample Collection:

Saliva will be collected from enrolled infants and parents non-invasively to evaluate the effects of KFC on established biomarkers of stress (cortisol and testosterone) and father-infant bonding (oxytocin). Before, during, and after each KC session, saliva will be collected from the participating parent, and their infant. A trained member of the study team will collect saliva from the infant using suction, a method that follows the standard of care for the infant, or oral swabs (27) made from an inert polymer and appropriately sized for an infant mouth (approximately 5 mm). Saliva samples will be taken from the infant immediately prior to beginning a KC session (T1), 30 minutes into the KC session (T2), and 30 minutes post-session (T3). Parents will self-collect saliva samples at the time points outlined above, using an adult-sized oral swab. At T2, the trained study team member will be able to help the parent collect the saliva sample, if necessary, while the parent continues to hold their infant. This approach to salivary sample collection and biomarker analysis is similar to that established by previous studies of kangaroo care (26,27) and takes into consideration the 30-minute delay before cortisol reactivity in saliva.

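### Infant 'before' and 'after' periods have no stated length and no record of non-study kangaroo care, so such care can be analysed as the reference period

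*Combined protocol and SAP*

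**What the plan says.** **Outcomes.** Section 2.2.1 uses infant heart rate and SpO2 as "indicators of cardiorespiratory stability in infants before, during, and after KC". Section 2.2.2 makes the same three-phase comparison for infant cortisol, and section 5.1 tests the biomarkers by repeated-measures ANOVA with phase as the repeated factor.

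**Eligibility.** Section 3.1.1 accepts infants who "are ≤20 days old at the time of enrollment". The exclusions in 3.1.2 concern conditions that would interfere with KC, for example "congenital anomalies or skin abnormalities deemed likely to impact KC by clinical team". Neither list mentions KC already given.

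**Sessions (3.3, Kangaroo Care Intervention).** Each family has one 2-hour session with the mother and one with the father, in random order. Consecutive days are the aim; otherwise sessions are held when the parents can come. They consist of "continuous skin-to-skin holding of the infant by the parent, per standard of care protocol". Section 1 says that "NICU implementation of KC typically involves the mother".

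**Measurement (3.3, Physiologic Recording and Saliva Sample Collection).** Infant sensors stay on for up to 48 hours. The parent's recording covers 1 hour either side of the session; no matching window is given for the infant. Saliva is taken just before the session (T1), then "30 minutes into the KC session (T2), and 30 minutes post-session (T3").

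No section sets a KC-free interval, describes a log of non-study KC, or names prior KC as a covariate.

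**The concern.** A before-during-after comparison needs reference periods that differ from the middle period in the exposure being studied. Here the exposure is also available as usual care, and the parents' visits, when sessions are held, are also when other holding can happen. An infant held by one parent shortly before the other parent's session, or handed over straight after it, contributes skin-to-skin time under the label 'before' or 'after'.

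The infant part of the primary outcome and the cortisol phase test are at stake. The gap cannot be repaired at analysis: contact that was never logged cannot be flagged, set aside or adjusted for. The open length of the infant windows adds a second freedom, since the analyst could choose them after seeing the recording.

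**Working it through.** The plan has no figure on this point to reproduce. Its statement of more than 99% power (end of section 5) comes with no sample size, effect size, standard deviation or intraclass correlation, so it cannot be recomputed, and nothing below depends on it.

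**1. How much infant recording is unprotected.** Two sessions of 2 hours give 4 hours of study KC. Of up to 48 recorded hours that is 4/48 = 8.3%. The other 44 hours carry no KC restriction or log, and the plan does not say which of them form the reference periods.

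**2. Effect on the phase contrast.** Let δ be the true during-minus-before difference and c the share of the reference window spent in non-study KC. Assume that this KC has the same full, immediate effect as study KC.
- Observed contrast = (1 − c)δ
- Sample-size multiplier to restore power = 1/(1 − c)²
- Power = Φ[(1.96 + z)(1 − c) − 1.96], where z is the normal quantile of the undiluted power (two-sided 5%, as in section 5.1)

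| c (assumed) | Minutes in a 1-hour window | Contrast kept | Sample-size multiplier | Power if 80% undiluted | Power if 99% undiluted |
|---|---|---|---|---|---|
| 10% | 6 | 90% | 1.23 | 71.3% | 97.1% |
| 25% | 15 | 75% | 1.78 | 55.6% | 89.5% |
| 50% | 30 | 50% | 4.0 | 28.8% | 57.3% |

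The documents give no value for c.

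**3. Saliva timing.** Count minutes from the start of a session. T1 is at about 0, T2 at 30, the session ends at 120, and T3 is at 120 + 30 = 150. The protocol allows for a 30-minute delay before cortisol reactivity shows in saliva.
- T1 therefore reflects roughly the half hour before the session, including any holding then.
- If the infant passes to the other parent at minute 120, T3 falls 30 minutes into new KC, the same position as T2, and is still analysed as 'post'. The same delay means that T3 partly reflects the end of the study session anyway, so the effect on T3 is less certain than on T1.

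**4. Prior KC by parent.** Suppose the outcome shifts by b per unit of earlier KC with the parent who is holding, and the mother has g units more than the father. Randomised order cancels a period effect, but the expected father-minus-mother difference still moves by −b·g. With b = 0.1 SD (assumed), a simulated two-period crossover with a period effect of 0.3 gave about 0.00, −0.10 and −0.30 SD for g = 0, 1 and 3. This shows that order does not balance such a gap. It does not show that a gap exists.

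**The case against.** **The amount may be small.** Section 1 calls KC heavily underused, and the reference to a standard-of-care protocol describes how holding is done, not how often or by whom. This stands: the share is unknown. It does not make the share zero, and without a record nobody could show that it was small.

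**A record may exist.** The content of the saliva questionnaires is not described and the covariate list in 2.2.2 is open-ended. So one can say only that no such item is described. No analysis that uses one is described either.

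**The bias need not be toward no effect.** The (1 − c) rule assumes equal, immediate effect and no carry-over. This also stands; the table is an illustration.

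**Stronger readings that the documents do not support:**
- *That the father-mother contrast carries unequal prior exposure.* The statement about mothers in section 1 is general background, not data on this unit. Each infant has both sessions, so its age at entry and total KC before the first session are shared; only the split between parents and KC between sessions can differ. No father-mother test of infant heart rate or SpO2 is named.
- *That prior KC far exceeds study KC.* An accumulated 10 to 40 hours needs an assumed 0.5 to 2 hours a day for the full 20 days. The documents give no rate.
- *That unlogged KC is why long-term questionnaire effects cannot be attributed to father KC.* Every family receives both sessions, so no arm is without it. A perfect log would not cure that.

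**Conclusion.** The concern holds for the reference periods. The infant windows for heart rate and SpO2 have no stated length, and the plan describes neither a restriction on nor a record of non-study skin-to-skin contact around or between sessions. As written, KC can be analysed as 'before' or 'after', and T1 or T3 can reflect other KC. That conclusion comes from the text alone.

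Its size does not. If non-study KC acts like study KC, the contrast shrinks in proportion to the share of the window affected, so 10% to 50% would leave 90% to 50% of it. Those shares are assumptions.

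A difference between mother and father in prior KC is a possibility that randomised order would not remove. It is a reason to collect the information, not a demonstrated bias.

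**What to change.** In section 3.3:
- Set the infant 'before' and 'after' windows for heart rate and SpO2 to 1 hour either side of each session, matching the parent recording.
- Log start, stop and parent for all non-study skin-to-skin contact from enrolment to the end of sensor recording.
- Record at enrolment the KC already given by each parent.

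In section 5.1:
- Label epochs and saliva samples that overlap or closely follow logged non-study KC, with the interval stated in advance. The 30-minute cortisol delay already in the protocol is a natural starting point for saliva.
- State whether labelled data are excluded in the main phase analysis or in a named sensitivity analysis.
- Use a mixed model for the saliva outcomes. With three samples per session, a complete-case repeated-measures ANOVA could lose the whole session when one sample is set aside.
- Report prior KC by parent descriptively. Use it as a covariate only in a sensitivity analysis of any father-mother comparison: if mothers do have more prior KC, it will be strongly correlated with parent and the adjustment will lean on model form.

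The cost is a short form, a bedside log, a few minutes of parents' or staff time, and some epochs or samples set aside. The KC that families give need not change.

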### 3.1.2. Exclusion Criteria

Infants: Infants who are intubated or sedated, are receiving vasopressors or analgesics, have any congenital anomalies or skin abnormalities deemed likely to impact KC by clinical team, have received or are planned to receive surgical intervention that will impact the utilization of KC, wearable sensors, and/or oral swabs, or are experiencing other symptoms or receiving other intervention that will impact the utilization of KC, wearable sensors, and/or oral swabs will be excluded from this study.

Parents: Parents who are showing any signs of illness or taking corticosteroids or testosterone supplementation will be excluded from this study. Non-English speaking parents will also be excluded from this study because the questionnaires associated with this study are only available in English.

## 3.2. Screening and Consent

Families who qualify for participation in this study will be identified through review of electronic medical records. Once a potential subject is identified, a study team member will consult the NICU care team in order to assess the condition of the infant and determine the family's approachability for discussion of the study. If the clinical care team feels a family is approachable, a member of the study team will identify the best time to meet with the family. All participation will be discussed at the infant's bedside in a private room.

During this discussion, the study team member will outline the following study details for the family: the rationale of the study, the specifics of data and specimen collection, the study team's legal and ethical obligations and practices to ensure confidentiality, the physiologic monitoring by wearable, wireless biosensor, the KC interventions, the salivary sample collection, the saliva questionnaires and the psychosocial questionnaires and follow-up. The study team member will also discuss the risks of participation, which include the risks of adverse reaction to the adhesive used on the wearable, wireless biosensors. The family will be informed that their commitment or refusal to participate will not affect the care their child receives in the NICU and will be completely optional and anonymous. A copy of the Informed Consent document will be provided to each family. The family will then be left with the consent form to review discuss privately. After this period of private review, the study team member will return and give parents the opportunity to ask questions. Once all questions are answered, the parents will be asked to describe the study process as they understand it in their own words. To minimize the amount of time the study team spends in the infant's bed space an infant's parent(s) may provide consent over the phone or a secure telecommunication platform such as Skype for Business. The consent process as described above will not change. The family will be provided written materials describing the nature of the optional elements and given an opportunity for questions and private discussion.

Consent obtained over the phone or secure telecommunication platform will be obtained according to institutional policy. A member of the study team will explain in detail and review the informed consent document(s) with the parent(s). If the parent(s) agree to participation, they will sign a copy of the informed consent document(s) and the study team member obtaining consent will sign a copy at the

same time. The parent(s) will be required to send their signed document(s) to the study team by mail, fax, or email, and the two signature pages will be combined. The parent(s) will be provided a copy of the fully executed, signed informed consent document(s) by mail, fax, or email prior to any study procedures.

## 3.3. Study Procedures

#### Screening:

Participants will be recruited from the NICU at Prentice Women's Hospital. A member of the study team will screen all NICU patients for inclusion and exclusion criteria by reviewing electronic medical records. A screening and enrollment log will be kept to track families who have been approached and agreed or declined to participate in the study. The screening and enrollment log will be kept on a secure REDCap server housed by Northwestern University. Only the study team will have access to this log.

#### Kangaroo Care (KC) Intervention:

After enrollment, families will be scheduled to participate in two sessions of KC. The goal will be to schedule the KC sessions over two sequential days and at approximately the same time of day (i.e. morning, afternoon, or evening). However, if this is not possible given the parents' schedules, the sessions will be scheduled for the days and time of day that participating parents are able to visit their infant in the NICU. Each session will include two hours of continuous KC, with one day focused on Kangaroo Mother Care (KMC) and the other on Kangaroo Father Care (KFC), in a randomized order. These sessions will include continuous skin-to-skin holding of the infant by the parent, per standard of care protocol.

#### **Physiologic Recording:**

*Infant*: Prior to the first scheduled KC session, two wearable, wireless biosensors will be placed on the infant to continuously capture physiology measures including electrocardiogram (ECG), heart rate (HR), oxygen saturation (SpO2), body temperature, respiratory rate, movement, systolic blood pressure (BP-S), and others for the duration of the study. One device will be placed on the infant's chest or back. A second device will be placed peripherally, on the infant's leg, foot, arm, or hand. The devices are encapsulated in a medical-grade silicone and will be adhered to the infant's skin using a medical-grade adhesive, similar to the adhesives standardly used in the NICU. The biosensors will be left in place for up to 48 hours, but will be checked by study staff at least once every 24 hours to ensure skin integrity and signal quality. The adhesives will be changed between uses.

**Parent:** The same type of wearable, wireless biosensor will also be used to record 4 hours of continuous physiology including ECG, HR, temperature, movement, SpO2, and others in the infant's parents. The biosensor will be placed on the parent's chest 1 hour before the start of a scheduled KC session and worn for 1 hour preceding the scheduled KC session, during the 2-hour KC session, and for 1 hour after the completion of the KC session. The biosensor will be worn by the parents for approximately 4 hours in total.

#### Skin Monitoring:

Before and after the wearable biosensors are placed on the infant, the infant's skin integrity will be evaluated using a neonatal skin scoring measure for monitoring skin integrity. Study staff will take

photographs of the skin at the site of biosensor placement before the biosensors are placed and after the biosensors are removed. Skin changes occurring while the biosensor is adhered to the infant's skin will be documented photographically. No faces will be photographed. The study team will consult the bedside care team within 1 hour for any changes in skin integrity (based on the neonatal skin integrity score).

#### Saliva Sample Collection:

Saliva will be collected from enrolled infants and parents non-invasively to evaluate the effects of KFC on established biomarkers of stress (cortisol and testosterone) and father-infant bonding (oxytocin). Before, during, and after each KC session, saliva will be collected from the participating parent, and their infant. A trained member of the study team will collect saliva from the infant using suction, a method that follows the standard of care for the infant, or oral swabs (27) made from an inert polymer and appropriately sized for an infant mouth (approximately 5 mm). Saliva samples will be taken from the infant immediately prior to beginning a KC session (T1), 30 minutes into the KC session (T2), and 30 minutes post-session (T3). Parents will self-collect saliva samples at the time points outlined above, using an adult-sized oral swab. At T2, the trained study team member will be able to help the parent collect the saliva sample, if necessary, while the parent continues to hold their infant. This approach to salivary sample collection and biomarker analysis is similar to that established by previous studies of kangaroo care (26,27) and takes into consideration the 30-minute delay before cortisol reactivity in saliva.

#### Saliva Questionnaires:

When saliva is collected from parents at time points T1, T2, and T3, parents will also be asked to complete a brief saliva questionnaire. These questionnaires will take approximately five minutes each to complete and will be completed on paper or directly in REDCap, depending upon the participant's preferences. At T2, a study team member will be able to help the parent complete the survey, if necessary, while the parent continues to hold their infant. Data provided on surveys completed on paper will be transferred to secure REDCap forms by study staff and destroyed within 24 hours. All questionnaire data will be stored long term on the secure REDCap server housed by Northwestern University.

